## **CONTROL GROUP**

Waiting list for SMS intervention: At the 12 month outcome assessment men will be offered an alternative SMS intervention for 3 months, based on the feedback received from intervention men at 3 months and qualitative interview data. At baseline, men will receive information (web or print) about weight loss and a pedometer. There will be no interim measurements or contacts by the research team. Men are therefore free to choose whether to try to lose weight or to self-monitor during the 12 months. They will not have access to the self-monitoring page on the study website until after the 12 month outcome assessment. The NIHR commissioning brief 14/185 asks for non-provision/usual practice. The control arm is as close as possible to "doing nothing", whilst remaining ethical (information, free choice to lose weight and later assistance via SMS to reduce disappointment bias). Men will be asked about their weight and any efforts they have made to change between enrolment and the 12 month assessment, and those choosing to receive alternative text messages will be followed up in person after 3 months using the same procedures as employed during the 3 months follow up of intervention participants.

## **ALL GROUPS**

Post randomisation, all men (intervention and control groups) will be provided with the standard NHS information on weight loss, other useful sources of information (web or print) and a pedometer with built in accelerometer as recommended for PA self-report. All participants will receive £20 reimbursement of expenses for attending the 12 month assessment.

## 4.4. COMPLIANCE AND LOSS TO FOLLOW-UP

Both interventions are centrally delivered, so fidelity of delivery is not an issue. Engagement with the interventions, retention and reasons for drop-out are described in Sections 4.5 and 4.6.

## 4.5. OUTCOME MEASURES

**Primary outcome:** A decision whether to proceed to a full effectiveness and cost-effectiveness RCT for the SMS intervention, with or without an incentive, compared to a waiting list control. This will be based on the progression criteria set out in Section 3. Criteria include quantitative and qualitative outcomes for:

- Acceptability of the interventions and the control group (willingness to be randomised, intervention engagement, participant retention, qualitative views)
- Feasibility of recruiting 105 obese men across socioeconomic and cultural spectra, intervention delivery, outcome measures at each time point, the potential for assessor blinding
- Evidence of positive indicative weight loss effects at 12 months for at least one group
- Feasibility of gaining consent for longer term follow up and NHS data linkage

## Secondary outcomes for this study:

Process data: differential recruitment, intervention engagement and retention by socioeconomic status, recruitment strategy (GP practice or community venues) and geographical area (deprivation index). Impact on quality of motivation (intrinsic and extrinsic), satisfaction with weight loss. Qualitative experiences, including acceptability of the incentive, the impact on social networks and families, need for additional support, unintended consequences e.g. incentive gaming, sustainability. Usual practice while on the waiting list will be described, and compared with each intervention group.

**Future full RCT- proposed primary outcome is:** mean difference in weight loss (absolute and percentage) between groups at 12 months.

**Future full RCT - proposed secondary outcomes** (may change depending on the findings of this study): waist circumference, QALYs, costs, cost-effectiveness. PhD studentship is investigating the feasibility of follow-up until 24 months and data linkage to routinely collected health outcomes, e.g. hospital admissions, obesity related diagnoses such as diabetes, cancers, heart disease, high blood pressure.

## 4.6. ASSESSMENT AND FOLLOW UP

Weight outcomes will be collected at baseline, 3, 6 and 12 months (standard time points in weight loss studies); these were acceptable in our survey of obese men and with our PPI group. Assessment at 3 months, will allow early identification (and rectification) of any problems with the trial design.

Assessments use validated tools where available and follow quality standards for measurement procedures. These are summarised in Table 1. More detail is provided in section 4.7

Table 1: Assessment schedule of essential and desirable variables according to male obesity programmes checklist from the Men's Health Forum (MHF)

Essential variables	0	3	6	12
Socio-demographics, co-morbidities, disability, ethnicity	✓			
Anthropometry (height, weight, BMI, waist circumference)	✓	✓	✓	✓
Mixed methods process/acceptability data	✓	✓	✓	✓
Lifestyle behaviours and activities (diet, PA, smoking, alcohol)	✓		✓	✓
Health Economic Outcomes: EQ-5D, NHS health care use	✓		✓	✓
Theory-based mediators	√	√	√	✓
Wellbeing	√			✓

Mixed methods data collection: will assess the acceptability and feasibility of different venues, recruitment strategies, randomisation, retention and outcome collection. We will collect i) numerical data on attendance at appointments, ii) monitor intervention engagement through response rates to SMS, iii) researchers will informally ask men how they are getting on with being in the study and collect field notes of participant experiences when collecting outcome data at 3 months, 6 months and 12 months. A purposive sample of diverse and information rich men will be invited to volunteer for longer semi-structured qualitative interviews (6-10 from each trial group) at 12 month assessments or at a separate appointment (participant choice: face to face, telephone, Skype). The qualitative interview sampling frame and topic guide will be modified iteratively according to the emerging analysis. Perceptions on the original texts and the alternative texts will be explored by showing men a sample of the texts that they have not received. Think-aloud techniques will be used to understand preferences for style and content. The researchers will complete a reflexive diary of participant discussions, which will contribute to the mixed methods data collection and analysis.

We will examine issues of sustainability and future implementation into practice throughout this study. We will explore sustainable and efficient ways to verify weight measurements, should the SMS plus incentive intervention show most promise.

**Follow up:** A PhD student funded by University of Stirling will follow up men from month 12 to 24, after the interventions have finished. She will assess the acceptability and feasibility for a future full trial of gaining consent to access routinely collected NHS data via data linkage and to contact participants in the future. Interest in participating in the follow up study until 24 months is included in the initial consent form and will be confirmed verbally at the 12 month assessment. Assessments will occur remotely at 24 months after the start of the intervention for intervention and waiting list control participants and at 12 months after the start of the intervention for the extra participants reviving alternative SMS. Qualitative semi-structured interviews with men and their family members/significant others will ask about men's experiences with their weight after the intervention stops and whether it would be acceptable and feasible in a future trial to link the results of this study to men's future medical records (e.g. diabetes, heart disease, high blood pressure, hospital admissions, medication). The actual data linkage will not be done by the student unless additional resource can be found (ethics amendment would be requested). The student's work will inform data linkage decisions in a

future full trial. The student will ask about any unintended consequences arising from the study or need for additional support.

Outcome data collection: The assessment of weight and other outcome measures will be undertaken by researchers in suitable venues for participants (identified in Phase 1). This may be done at the participant's home if that is the only suitable venue for that participant. However, we are keen to encourage attendance at a community venue as this is a more sustainable model for the future. Men in the two intervention groups will receive an appointment and a SMS reminder at 3m, 6m and 12m (control group 12m only) to attend weight assessments. Non-attenders will receive two reminders to make contact with the researchers and given the opportunity to arrange another appointment. Reminders will use different methods e.g. SMS, email, phone, because mobile phone numbers change and harder to reach men may run out of phone credit. Researchers will use a portable stadiometer (height), measuring tape (waist circumference) and calibrated scales (weight) electronically linked by Bluetooth to a computer to transmit data directly to TCTU databases (manual systems as backup). Hard copies for all participant anthropometric measurements will also be noted to prevent any missing data caused by technology failure. The feasibility of offering both direct participant entered data onto a computer or paper version will be explored. Either the participant (with the researcher present for assistance) will enter the questionnaire data directly or the researcher will enter the data from completed paper versions of the questionnaire into the tablet (participant preference). All participants will be offered a £20 reimbursement to attend final 12 month outcome measures. Such reimbursements have been shown to increase follow-up rates.

The Delegation of Responsibilities Log will identify all trial personnel responsible for data collection, entry, handling and managing the database.

Towards the end of recruitment, we will attempt to assess the feasibility of blind outcome assessment. Researchers will remind men not to disclose which group they are in. One researcher who has not met the participant at enrolment will undertake either the 3, 6 or 12 months outcome assessments and will see if men reveal which group they are in. In a future trial, the feasibility of researchers being independent of the research team for blind outcome assessment and managed by SPCRN will be considered.

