**HOW (Mode of Delivery)**: Men's preferences of direct bank transfer (self or charity donation) or secure postage of a cheque will be ascertained at the 12 month assessment. In our survey, 11% of the 1045 obese men would choose a charity donation.

WHERE: Weight goal verification will be in suitable venues with subsequent SMS notification.

**WHEN and HOW MUCH**: (See Box 2) At 12 months participants will receive money depending on weight loss achievements. PPI consultation recommended no interim payments. The logistics for paying men and the future sustainability of the programme support this.

PERSONALISING INCENTIVES Men will lose money if they do not reach weight loss targets. Men can choose the incentive purpose at each time point (money for oneself vs. for charity) and the weight loss target after the 3 months' assessment. The men in the SMS with incentives arm of the trial will have an additional web page explaining the incentive scheme and providing a visual chart to provide feedback on their incentive progress. All other elements will be the same as for the SMS only group, including a website chart (paper available if no web access) of the weight loss targets at 3, 6 and 12 months.

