## 4.9. SAMPLE SIZE

Feasibility RCT: We aim to randomise 105 men, 35 to each arm, in line with recent recommendations for pilot trials as sufficient to estimate key parameters for a full trial. We will conduct 18-30 face to face or telephone interviews (6-8 men from each trial group) recruited throughout the trial. This sample size is based on previous experience of conducting feasibility studies like this. A sampling frame will ensure diversity for socio-demographic and personal weight loss histories.

Mixed methods process evaluation: All men (n=105) who attend the 12 month assessment will be asked an open question for any suggestions for improving the study. Men who do not attend will be sent a final "thank you" letter informing them of how they can access the findings, and will be invited to provide feedback. Based on previous research experience of applying qualitative research in feasibility RCTs, 18-30 qualitative semi-structured interviews, with a diverse and information rich sample (6-10 from each trial group) are likely to be required to reach data saturation for key themes and for no new thematic issues to arise in interviews. However, some flexibility in the precise sample size is required, as it is impossible to predict important research questions that might arise in a complex intervention study like this. The PhD student will also conduct an additional 18-30 semi-structured interviews to investigate variation in engagement of men and to find out about their experiences after the intervention has finished.

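### The assessor-blinding check may be done at 3 or 6 months, when no control attends, and nothing ensures it is done at 12 months, the only visit that can test blinding against waiting list

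*Protocol*

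**What the plan says.** The blinding check is described in Protocol section 4.6, under outcome data collection. It opens with "Towards the end of recruitment, we will attempt to assess the feasibility of blind outcome assessment". Men are to be reminded not to disclose their group. Then "One researcher who has not met the participant at enrolment will undertake either the 3, 6 or 12 months outcome assessments", and that researcher "will see if men reveal which group they are in". No other observation is specified for the check.

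The same paragraph sets the visit schedule by arm: "Men in the two intervention groups will receive an appointment and a SMS reminder at 3m, 6m and 12m (control group 12m only". The Control group part of section 4.3 confirms it for the period before 12 months: "There will be no interim measurements or contacts by the research team".

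The check has a stated role. Section 1b lists feasibility of assessor blinding among the primary outcomes. Section 4.5 includes "the potential for assessor blinding" among the feasibility items that inform the decision on a full trial.

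Several tasks at the 12-month visit depend on the arm. For incentive men, the preference between bank transfer and "secure postage of a cheque will be ascertained at the 12 month assessment" (section 4.3, Intervention 2). Controls are offered the alternative texts at that visit (section 4.3, Control group). The protocol does not say whether weighing comes before or after these tasks.

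**The concern.** A blinding check is informative about a contrast only if men from both sides of it can appear before the assessor. At 3 and 6 months the waiting-list arm is absent by design. A man who says nothing at such a visit would count as not having revealed his group, yet the assessor already knows that he is not a control.

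The full trial's main question (section 3) compares the interventions with waiting list, and its proposed primary outcome is weight loss at 12 months (section 4.5). If most or all checks fall at 3 or 6 months, a low disclosure rate could be reported as showing that blind assessment is feasible when blinding against control was never tested. That conclusion would pass into the design of the full trial. An analysis plan cannot repair this, because it cannot supply controls who were not seen.

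**Working it through.** The protocol gives no power or sample size figure for the blinding check. The only figure to reproduce is the total: "We aim to randomise 105 men, 35 to each arm", and 3 × 35 = 105, which agrees.

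**Inputs**
- Arm size: 35 per arm (section 4.9).
- Visits: intervention arms at 3, 6 and 12 months; controls at 12 months only (section 4.6; section 4.3, Control group).
- Visits at which the check may be made: 3, 6 or 12 months (section 4.6).

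**Scheduled attendance and what it reveals**

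P(intervention | attends) = (SMS + SMS plus incentive) / all scheduled to attend.

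| Visit | SMS | SMS + incentive | Control | Total | P(intervention, given attendance) |
|---|---|---|---|---|---|
| 3 months | 35 | 35 | 0 | 70 | 70/70 = 1.00 |
| 6 months | 35 | 35 | 0 | 70 | 70/70 = 1.00 |
| 12 months | 35 | 35 | 35 | 105 | 70/105 = 0.667 |

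Total scheduled follow-up visits: 70 + 70 + 105 = 245. Visits at which attendance alone excludes control: 70 + 70 = 140. Share: 140/245 = 57%.

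**Sensitivity to drop-out.** The share does not change if retention is the same in all arms and at all visits. At the 72% per-group progression threshold (section 3), 0.72 × 35 = 25.2, so at least 26 men per arm are needed. Then 4 × 26 = 104 of 7 × 26 = 182 visits, again 57%.

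**What remains testable.** At 3 and 6 months the two intervention arms are 35:35, so SMS versus SMS plus incentive is still 50:50 to an assessor who knows only that the man attended. At 12 months all three arms attend, so attendance reveals nothing about arm.

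**Could another passage rescue the 3 or 6 month check?**
- The opening of section 4.6 lists weight collection at 3, 6 and 12 months without separating the arms. The explicit statements in the same section and under Control group settle that controls are excepted.
- Men on the alternative texts also have a 3-month visit. For controls it follows their 12-month outcome, and the additional men recruited under section 4.2 (vii) are outside the three-arm randomisation. Neither helps.

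**The case against.** The strongest reply is that the valid visit is already in the plan: 12 months is one of the three named options. That stands, so it would be wrong to say that the protocol excludes controls from the check. The fault is narrower: the wording allows the check to be done wholly at 3 or 6 months and does not separate the results by visit.

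The early visits also have value. Whether incentives add to texts is a stated interest (sections 1a and 3), and section 4.6 values the 3-month assessment for finding design problems early. That stands too. The early checks need not be dropped, only labelled for what they can show.

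Three stronger readings are tempting but not supported:
- *Only 3-month visits can be used, because the check is timed near the end of a 4-month recruitment period.* The same paragraph names 6 and 12 months, neither of which could fall inside 4 months. The phrase may well describe when the exercise starts.
- *An assessor at 3 or 6 months would guess correctly every time.* That is true only of a two-way guess, intervention or control. The plan concerns which of three groups a man is in, and always naming one intervention arm would be right about half the time.
- *72% is the expected retention, so about 75 men would be available at 12 months.* It is a per-group minimum for progression. Just meeting it means 26 in each arm, or 78 men, and only those seen by a researcher who did not enrol them would count.

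On task order at 12 months, the protocol does not say that payment preference is raised before weighing or by the same person, and such detail is often left to working instructions. The point is therefore conditional. Transmission of weight by Bluetooth also limits an assessor's influence on that outcome, but it does not answer whether blinding is feasible, which is what the check is for.

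Finally, assessor blinding is not itemised among the six progression criteria in section 3, and no estimate in this study depends on it. That limits the weight of the point without removing it, since sections 1b and 4.5 both name blinding within the primary outcome.

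**Conclusion.** The point holds in this form. At two of the three permitted visits, covering 140 of 245 scheduled visits (57%), attendance alone shows that a man is in an intervention arm. A check there can inform only SMS versus SMS plus incentive. Blinding for the comparison with waiting list can be tested only at 12 months, and the plan does not ensure that any check is made then.

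This rests on the schedule as written, with controls attending at 12 months only, and on equal allocation. The 57% assumes full attendance or equal retention across arms and visits. The conclusion about 3 and 6 months needs no retention assumption, since no controls are scheduled then. It does not depend on how the timing phrase is read.

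The change is worth making because it is cheap and determines what the study can conclude about blinding. It does not affect the study's other estimates.

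**What to change.** Amend the blinding paragraph in section 4.6 as follows:

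1. The intervention-versus-control check is made at the 12-month visit, in all three arms, by the already planned researcher who did not enrol the man.
2. At that visit the man is weighed, and the assessor records a guess of arm (control, SMS, SMS plus incentive, or don't know) and whether the man disclosed it. This is completed before payment preference, the offer of alternative texts, or any other item that reveals allocation is raised.
3. Any results from 3 or 6 months are reported separately and described as SMS versus SMS plus incentive only.

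A formal blinding index is optional; correct guesses and disclosures by arm would serve a feasibility study.

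The cost is protocol wording, a short form entry and a fixed order of tasks. No new visit is needed. The protocol does not give the number of researchers, so the sponsor should confirm that one who did not enrol the man can be scheduled at 12 months. The drawback is that the control-contrast result comes later and from fewer visits: at most 105 at 12 months, against 245 across all three time points.

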## 4.7. ASSESSMENT OF OUTCOME MEASURES FOR THE FEASIBILITY RCT

The following outcome assessments are based on existing research evidence, PPI and findings from Phase 1 of our study, with timing detailed in Table 1:

- Anthropometry (weight, waist circumference)
- Acceptability: Satisfaction with intervention overall, materials, and delivery.
- Lifestyle behaviours: including PA, Diet, Alcohol consumption and smoking
- Wellbeing and Quality of Life: Warwick Edinburgh Mental Wellbeing Scale, EQ-5D
- Theory-based mediators of behaviour change including motivational quality [intrinsic vs. extrinsic], and satisfaction with behaviour change and weight change
- Health Economic outcomes: QALYs, NHS costs for future cost-effectiveness analysis

We will identify core outcomes that matter for obese men in a future full RCT and that are valid, acceptable and feasible through PPI consultation qualitative interviews.

Process evaluation measures which will be triangulated by qualitative data:

- Willingness to be randomised (assessed by reporting the numbers: approached; recruited, randomised, attending assessments, drop outs and reasons)
- Engagement with the interventions (including SMS components [i.e. number of SMS exchanged], incentive component [i.e. amounts awarded], number of self-report measurements e.g. weights, pedometer readings and hit rates for the study website information menus and visual feedback of progress towards targets
- Deviations from the intended intervention (technical factors relevant to sustainability)

## 4.8. ASSESSMENT OF UNEXPECTED CONSEQUENCES

Participants will be asked to report unexpected consequences from participating in the study, although systematic reviews of SMS or incentive interventions would suggest these are unlikely..

Safeguarding for research participants is important. This is a very low risk study, however there is a possibility that men who are unsuccessful in their weight loss attempts may become upset and that this could impact on their emotional well-being. The researchers will be sensitive to this. In very rare circumstances, if the safety of the participant or of another person was thought to be at risk, the researcher would breach confidentiality. For example if a man told a researcher that he felt suicidal. Under these circumstances, the researcher would speak to the study leads or a senior member of staff in the host institution as soon as possible and in discussion with the participant the next steps would be agreed. The co-chief investigator, [name], is a GP and is therefore trained to manage such situations. Patient information leaflets (web and print) and SMS information which will provide local and national contacts where men can access additional support. The Health Informatics Centre in Dundee have experience of automatically screening incoming text messages in similar studies for words like suicide, die, death. The study will use these tried and tested procedures. If a worrying SMS message is identified, the researchers will discuss this with a senior colleague and a plan would be agreed, which may or may not involve alerting appropriate services, following on a risk assessment.

Safeguarding the safety of researchers is also important. The researchers may work in pairs when recruiting or work alone, according to the neighbourhood and as advised by stakeholders with local knowledge. The Lone Worker Policy for staff working at the University of Stirling will be followed which includes informing a member of staff where and when research tasks are being carried out in the community, contact details and agreed report back times.

